### **6.1.1.2 Serious Adverse Events**

If an adverse event meets any of the following criteria, it is to be reported to AbbVie as a serious adverse event (SAE) within 24 hours of the site being made aware of the serious adverse event.

Death of Subject	An event that results in the death of a subject.
Life-Threatening	An event that, in the opinion of the investigator, would have resulted in immediate fatality if medical intervention had not been taken. This does not include an event that would have been fatal if it had occurred in a more severe form.
Hospitalization or Prolongation of Hospitalization	An event that results in an admission to the hospital for any length of time or prolongs the subject's hospital stay. This does not include an emergency room visit or admission to an outpatient facility.
Congenital Anomaly	An anomaly detected at or after birth, or any anomaly that results in fetal loss.
Persistent or Significant Disability/Incapacity	An event that results in a condition that substantially interferes with the activities of daily living of a study subject. Disability is not intended to include experiences of relatively minor medical significance such as headache, nausea, vomiting, diarrhea, influenza, and accidental trauma (e.g., sprained ankle).

**Important Medical Event Requiring Medical or Surgical Intervention to Prevent Serious Outcome**

An important medical event that may not be immediately life-threatening or result in death or hospitalization, but based on medical judgment may jeopardize the subject and may require medical or surgical intervention to prevent any of the outcomes listed above (i.e., death of subject, life-threatening, hospitalization, prolongation of hospitalization, congenital anomaly, or persistent or significant disability/incapacity). Additionally, any elective or spontaneous abortion or stillbirth is considered an important medical event. Examples of such events include allergic bronchospasm requiring intensive treatment in an emergency room or at home, blood dyscrasias or convulsions that do not result in inpatient hospitalization, or the development of drug dependency or drug abuse.

For serious adverse events with the outcome of death, the date and cause of death will be recorded on the appropriate case report form.

**6.1.1.3 Adverse Events of Special Interest**

Some adverse events, such as adverse events of special interest (AESI), such as rash/hypersensitivity, fracture, neuro-psychiatric (depression, mood swings, etc.), vasomotor symptoms (hot flush, night sweats) or serious adverse events. AbbVie may require additional information, including family history, to be collected and recorded in the eCRF.

**6.1.2 Adverse Event Severity**

The Investigator will use the following definitions to rate the severity of each adverse event:

- |                 |   |
|-----------------|---|
| Mild     | The adverse event is transient and easily tolerated by the subject.   |
| Moderate | The adverse event causes the subject discomfort and interrupts the subject's usual activities.  |
| Severe   | The adverse event causes considerable interference with the subject's usual activities and may be incapacitating or life-threatening. |

### 6.1.3 Relationship to Study Drug

The investigator will use the following definitions to assess the relationship of the adverse event to the use of study drug:

Reasonable Possibility	An adverse event where there is evidence to suggest a causal relationship between the study drug and the adverse event.
No Reasonable Possibility	An adverse event where there is no evidence to suggest a causal relationship between the study drug and the adverse event.

For causality assessments, events assessed as having a reasonable possibility of being related to the study drug will be considered "associated." Events assessed as having no reasonable possibility of being related to study drug will be considered "not associated." In addition, when the investigator has not reported a causality or deemed it not assessable, AbbVie will consider the event associated.

If an investigator's opinion of no reasonable possibility of being related to study drug is given, an "Other" cause of event must be provided by the investigator for the serious adverse event.

[figure not shown]
### 6.1.4 Adverse Event Collection Period

All adverse events reported from the time of study drug administration through Month 12 in the Post-Treatment Follow-Up Period, (if applicable) will be collected, whether solicited or spontaneously reported by the subject. In addition, serious adverse events and protocol-related nonserious adverse events will be collected from the time the subject signed the study-specific informed consent.

If a subject prematurely discontinues from the study, i.e., either prematurely discontinues from Treatment Period and does not enter the Post-Treatment Follow-Up Period or prematurely discontinues from the Post-Treatment Follow-Up Period, adverse events and serious adverse events will be collected up to 30 days after the last dose of study drug.

Adverse event information will be collected as shown in [Figure 5](#).

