**Post-Treatment Follow-Up Period:**

For subjects entering the 12-Month Post-Treatment Follow-Up Period, visits will be conducted either by phone or on-site from Month 1 through Month 12.

During the Phone Visits, Site Personnel will discuss adverse events, concomitant medications, if applicable, obtain the results of the subject's self-administered urine pregnancy test and will remind subjects of the importance of consistent use of appropriate and effective dual non-hormonal contraception through the Post-Treatment Follow-Up Period. Subjects may begin taking hormonal contraception or Tranexamic Acid (Lysteda, Cyklokapron, Cyclo-f) after completing the Post-Treatment Follow-Up Month 2 Visit and return to first full menses in the Post-Treatment Follow-Up Period.

Subjects will be required to collect sanitary products through their first menses with full menstrual flow in the Post-Treatment Follow-Up Period. Subjects will return the sanitary products at a Product Collection Visit within approximately 5 days after cessation of bleeding or spotting.

During the On-Site Visits, procedures such as TAU, TVU, MRI (if applicable), DXA, clinical safety labs and pregnancy testing will be performed. At the Post-Treatment Follow-Up Period Month 12 Visit, procedures including vital signs, lipid panel, Apolipoprotein A and B and DXA will be performed.

Adverse event and concomitant medication review will be conducted at all visits during the Post-Treatment Follow-Up Period, including the Phone Visits.

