**Figure 3. Management of BMD % Decrease: Post-Treatment Follow-Up Month 12**

Note: If criteria is not met, no referral to bone specialist is required.

The baseline DXA is the Screening DXA performed in the respective Pivotal Study M12-815 or Study M12-817. In the event that there is a change in DXA machine for a subject between baseline and a subsequent time-point, the AbbVie TA MD must be consulted.

A BMD decrease at any anatomic location (spine, total hip or femoral neck) during the Treatment or Post-Treatment Follow-Up Period that leads to premature discontinuation from study or a BMD decrease at any anatomic location with a T-score < -1.5 should be reported as an adverse event.

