## **6.1.1 Definitions**

### **6.1.1.1 Adverse Event**

An adverse event (AE) is defined as any untoward medical occurrence in a patient or clinical investigation subject administered a pharmaceutical product and which does not necessarily have a causal relationship with this treatment. An adverse event can therefore be any unfavorable and unintended sign (including an abnormal laboratory finding), symptom, or disease temporally associated with the use of a medicinal (investigational) product, whether or not the event is considered causally related to the use of the product.

Such an event can result from use of the drug as stipulated in the protocol or labeling, as well as from accidental or intentional overdose, drug abuse, or drug withdrawal. Any worsening of a pre-existing condition or illness is considered an adverse event.

Worsening in severity of a reported adverse event should be reported as a new adverse event. Laboratory abnormalities, and vital signs are considered to be adverse events only if they result in discontinuation from the study, necessitate therapeutic medical intervention and/or if the investigator considers them to be adverse events.

An adverse event of amenorrhea will be reported for subjects who do not return to menses by the Post-Treatment Follow-Up Month 2 Phone Visit and the adverse event will be followed until resolution. The onset date of the adverse event will be the date of the Follow-Up Month 2 Visit.

A BMD decrease at any anatomic location (spine, total hip or femoral neck) during the Treatment or Post-Treatment Follow-Up Period that leads to discontinuation from study or a BMD decrease at any anatomic location with a T-score  $< -1.5$  should be reported as an adverse event.

An elective surgery/procedure scheduled to occur during a study will not be considered an adverse event if the surgery/procedure is being performed for a pre-existing condition and the surgery/procedure has been pre planned prior to study entry. However, if the pre-existing condition deteriorates unexpectedly during the study (e.g., surgery performed

earlier than planned), then the deterioration of the condition for which the elective surgery/procedure is being done will be considered an adverse event.

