### **8.1.8.2 Adverse Events**

Adverse events (AEs) will be coded using the Medical Dictionary for Regulatory Activities (MedDRA) dictionary. Treatment-emergent adverse events (TEAEs) will be summarized for each treatment group. TEAEs are defined as AEs with a start date on or after the first dose of the study drug and within 30 days of the last dose of the study drug in the Extension Study. AEs starting more than 30 days following discontinuation of the study drug will not be included in the summaries of TEAEs. AEs starting more than 30 days following discontinuation of the study drug will be summarized separately as Post-Treatment AEs.

When summarizing TEAEs by relationship or severity, if a subject has an event with unknown severity or relationship, then the subject will be counted in the severity/relationship category of "unknown," even if the subject has a second occurrence of the same event with a severity/relationship present. The only exception is if the subject has a second occurrence of the same event with the most extreme severity (i.e., "severe") or a relationship category of "reasonable possibility." In this case, the subject will be counted under these most extreme severity/relationship categories.

The frequencies and percentages of subjects with TEAEs will be calculated for each treatment group as follows:

- Any event
- By system organ class, and preferred term
- By system organ class, preferred term and maximum relationship
- By system organ class, preferred term and maximum severity
- Any event and by system organ class and preferred term for events resulting in study drug discontinuation
- Any event and by system organ class and preferred term for serious events
- Any event and preferred term for AESI's (e.g., hypoestrogenic adverse events)

The Post-Treatment AEs will be summarized in a similar manner as the TEAEs described above.

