12.2.1 Analysis of Adverse Events in the Extension Study

Adverse events (AEs) in the extenstion study will be summarized using system organ classes (SOCs) and preferred terms (PTs) from the Medical Dictionary for Regulatory Activities (MedDRA) Version 19.0 or higher by the six analysis groups as described in Section 5.3.

For each AE summary, the number and percentage of subjects experiencing at least one AE will be presented. Subjects reporting more than one AE within a SOC will be counted only once for that SOC. Subjects reporting more than one AE for a PT will be counted only once for that PT.

Treatment-emergent AEs are defined as AEs with a start date on or after the first dose of study drug in the extension study. AEs starting more than 30 days following discontinuation of study drug will not be included in summaries of treatment-emergent

COBVIE Elagolix (ABT-620) M12.816 - Statistics

Elagolix (ABT-620) M12-816 – Statistical Analysis Plan Version 2.0 – 24 May 2018

AEs. Post-Treatment AEs are defined as AEs starting more than 30 days following discontinuation of study drug in the Treatment Period of this study.

When summarizing AEs by relationship or severity, if a subject has an event with unknown severity or relationship then the subject will be counted in the severity/relationship category of "unknown" even if the subject has a second occurrence of the same event with a severity/relationship present. The only exception is if the subject has a second occurrence of the same event with the most extreme severity (i.e., "severe") or the most extreme relationship category (i.e., "reasonable possibility"). In this case, the subject will be counted under these most extreme severity/relationship categories.

Treatment Period

The number and percentage of subjects with treatment-emergent AEs will be calculated by analysis group as follows:

- Any AEs
- Any AEs by primary MedDRA system organ class (SOC) and preferred term (PT)
- Any AEs occurring in ≥ 5% of subjects by primary MedDRA system organ class (SOC) and preferred term (PT)
- Any AEs by PT in descending frequency of 12 month elagolix 300 mg BID plus E2/NETA treatment group
- Any AEs by maximum severity (by primary MedDRA SOC and PT)
- Any AEs by maximum relationship (by primary MedDRA SOC and PT)
- Any AEs reasonably possibly related to study drug (by primary MedDRA SOC and PT, by PT)
- Any AEs leading to study drug discontinuation (by primary MedDRA SOC and PT)

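### Read literally, protocol 6.1.4 ends AE and SAE collection 30 days after the last dose for women who leave follow-up, in conflict with the rest of the protocol, so Post-Treatment AEs may be under-collected

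*Protocol*

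**What the plan says.** Protocol Section 6.1.4 contains two collection rules.

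- General rule, first paragraph: the period covers "All adverse events reported from the time of study drug administration through Month 12 in the Post-Treatment Follow-Up Period", where applicable.
- Rule for early leavers, second paragraph: it covers women who stop in the Treatment Period and never enter follow-up, and also any woman who leaves the Post-Treatment Follow-Up Period early. For both, "adverse events and serious adverse events will be collected up to 30 days after the last dose of study drug". The clock starts at the last dose, not at exit.

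The analysis definition uses the same 30 days from the other side. Protocol Section 8.1.8.2 states that "AEs starting more than 30 days following discontinuation of the study drug will be summarized separately as Post-Treatment AEs". SAP Section 12.2.1 agrees: "Post-Treatment AEs are defined as AEs starting more than 30 days following" discontinuation of study drug. Neither definition excludes women who leave follow-up.

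Other parts of the protocol expect AE capture well beyond day 30:

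- Synopsis, Post-Treatment Follow-Up Period: "Adverse event and concomitant medication review will be conducted at all visits during the Post-Treatment Follow-Up Period, including the Phone Visits".
- Section 5.4.1: a woman who leaves follow-up should have a Post-Treatment Premature Discontinuation Visit with the Appendix C procedures. The Appendix C follow-up schedule has an AE monitoring row and a column for that visit.
- Section 6.1.1.1: "An adverse event of amenorrhea will be reported for subjects who do not return to menses by the Post-Treatment Follow-Up Month 2 Phone Visit", with the onset date fixed at that visit.
- Section 5.3.1.1, note under Figure 3 (repeated in substance in 6.1.1.1): a BMD decrease "during the Treatment or Post-Treatment Follow-Up Period that leads to premature discontinuation from study" is to be reported as an AE.
- Section 6.1.6: a woman who becomes pregnant in follow-up is discontinued, and an abortion, stillbirth or congenital anomaly is an SAE to be reported within 24 hours.

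**The concern.** A 30-day limit suits a woman who stops treatment and is not followed further. Applied to a woman who has entered follow-up, it points to a date that has usually gone by when she leaves. A site that takes the section on the AE collection period at its word could decline to enter an event from month 5 that is first reported at the exit visit. A site working from Appendix C would enter it.

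Section 5.1 names the assessment of general safety and recovery over 12 months off treatment among the study's aims. SAP 12.2.1 reports Post-Treatment AEs and SAEs as numbers and percentages of women, and the Safety Analysis Set (SAP 5.1) contains every woman who took a dose. Leavers therefore stay in the denominator whether or not their late events were entered. Under-collection would lower the reported percentages and could differ from site to site.

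**Working it through.** The plan gives no figure to reproduce here. The check is day arithmetic on the visit schedule, followed by a comparison of the rules.

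**Inputs.** A month is 28 days (protocol, Definition of Terms). Follow-up lasts 12 months, with visit windows of ±7 days (protocol Table 1). Days are counted from the last dose (SAP 7.3). The cut-off is day 30 (6.1.4).

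**Step 1: how much of follow-up lies after the cut-off.** Follow-up lasts 12 × 28 = 336 days. Of these, 336 − 30 = 306 fall after the cut-off, and 306/336 = 91%.

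**Step 2: which visits lie after it.** Month 1 has its window at 28 ± 7, days 21 to 35, which straddles day 30. Month 2 has 56 ± 7, days 49 to 63, wholly after it. The same holds for every later visit up to Month 12 (336 ± 7, days 329 to 343). So 11 of the 12 visits lie wholly after the cut-off.

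**Step 3: overlap with the analysis definition.** Under the literal sentence, a leaver's collected events have onset on day 30 or earlier. Post-Treatment AEs have onset after day 30. No day satisfies both.

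**Step 4: what collection to exit would give.** The Post-Treatment AE window would run from day 31 to the exit day, a length of 28 × (exit month) − 30 days.

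| Exit at follow-up month | Window if collected to exit | Window under the literal sentence |
|---|---|---|
| 2 | 56 − 30 = 26 days | 0 |
| 3 | 84 − 30 = 54 days | 0 |
| 6 | 168 − 30 = 138 days | 0 |
| 9 | 252 − 30 = 222 days | 0 |
| 11 | 308 − 30 = 278 days | 0 |

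The middle column is the span that the sentence excludes on its face. It is not the amount of data lost, because events from earlier visits will already have been recorded.

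**Step 5: the other rules against the sentence.**

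- Amenorrhea: onset is fixed at the Month 2 visit, nominal day 56. Every such AE starts after day 30.
- BMD decrease leading to discontinuation: the scheduled follow-up DXA scans are at Months 6 and 12, nominal days 168 and 336.
- Pregnancy in follow-up: the woman is discontinued, and the outcome that makes an SAE will usually come after both day 30 and her exit. Section 5.4.1 allows her no further study procedures except an ultrasound, so the exit visit cannot be relied on to capture it.
- Exit visit: for anyone leaving after day 30, an AE review at that visit has no purpose if collection has already closed.

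Each rule requires capture that the 30-day sentence, taken alone, rules out. None makes an exception for women who later leave.

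**The case against.** The strongest reply is that little is lost in practice. AEs are recorded prospectively. At Month 4 a site cannot know that a woman will leave at Month 5, and what it has entered stays entered. No section calls for deletion, and the Post-Treatment AE definitions depend on onset date alone. The protocol also provides for an exit visit with AE monitoring, makes a BMD decrease that leads to leaving a reportable AE, and has the investigator follow AEs that are ongoing at exit (5.4.1). For a woman who leaves by about day 30, the sentence works as an ordinary minimum window.

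These points stand, and they rule out a stronger reading that the definitions invite. A reader might infer that leavers contribute no Post-Treatment AEs at all, and that the event that made them leave is necessarily lost. The documents do not support that. It would require recorded events to be discarded, and it passes over the rules that call for capture at exit.

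The reply does not rescue the sentence. If it only says how long collection continues after exit, then for anyone leaving after day 30 it either closes collection or does nothing. Pregnancy outcomes after exit remain in direct conflict with it.

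Two limits on the evidence also stand. Figure 5, to which 6.1.4 refers, and Section 6.1.5 were not in the text available for this check, and either might show the intended reading. Neither would remove the conflict in the written text of 6.1.4.

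**Conclusion.** Section 6.1.4 is wrong as written for women who leave follow-up after day 30. It contradicts its own first paragraph, the follow-up visit schedule, and the amenorrhea, BMD and pregnancy-outcome rules. Post-Treatment AEs and SAEs may be under-collected among leavers, chiefly events first reported at or around exit. Any resulting bias would be downward.

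The size cannot be computed, because neither document gives the number of women expected to leave follow-up. A reader might multiply an assumed dropout rate by the windows in the table and call the product lost follow-up. That would be a ceiling under the literal reading only, since it treats events already recorded as missing.

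Nor do the documents show that the loss would fall mainly on bone loss or persistent amenorrhea. The withdrawal list in Section 5.4 names neither. Bone recovery is analysed from DXA (SAP 12.4.2) and return of menses from alkaline hematin and UBQ data (SAP 11.3.5.4), so those analyses do not depend on the AE cut-off.

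**What to change.** Amend the second paragraph of 6.1.4 in three respects:

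1. For subjects who discontinue during the Post-Treatment Follow-Up Period, collect AEs and SAEs through the follow-up Premature Discontinuation Visit (or last contact) or 30 days after the last dose, whichever is later.
2. Keep the 30-day limit on its own only for subjects who never enter follow-up.
3. State that SAE reporting of pregnancy outcomes under 6.1.6 is unaffected.

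Align Figure 5 with the new text.

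The cost is about one sentence and a note to sites. The exit visit already exists and already includes AE monitoring. Post-Treatment AE percentages may rise slightly. The SAP definition needs no change. Showing event rates per woman-year beside the percentages is a separate presentation choice that this correction does not require.

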### **6.1.6 Pregnancy**

Pregnancy in a study subject must be reported to AbbVie within 1 working day of the site becoming aware of the pregnancy. Subjects who become pregnant during the Treatment or Post-Treatment Follow-Up Periods of the study must be discontinued (Section 5.4 and Section 5.4.1). A positive urine pregnancy test result must be confirmed with a serum pregnancy test. If a serum pregnancy test result is positive at any time during the Treatment Period of the study, the site will immediately inform the subject to discontinue study drug. Information regarding a pregnancy occurrence in a study subject and the outcome of the pregnancy will be collected for any study subject with a positive serum pregnancy test from the signing of the informed consent through the Post-Treatment Follow-Up Period. The site will report a positive pregnancy test to the Sponsor, will follow the course of the subject's pregnancy, and report to the Sponsor on the health of the subject and fetus at each trimester and at the first post-delivery pediatrician visit.

If the subject becomes pregnant during the Treatment or Post-Treatment Follow-Up Periods of the study, an ultrasound examination will be performed as early as possible during the first trimester of pregnancy to assess the conception date and document an intrauterine pregnancy. The following information on the outcome of the pregnancy that occurred after signing of the informed consent, regardless of when the subject became pregnant (i.e., either during the Treatment or Post-Treatment Follow-Up Periods) should be collected: fetal outcome (e.g., spontaneous or elective abortion, live infant or still birth), date of delivery, birth weight, birth length, gender, birth defects, congenital anomaly and medically significant complications during pregnancy or labor or delivery. For live infant births, information on the health of the infant will be collected 6 to 12 months after delivery.

Pregnancy in a study subject is not considered an adverse event. However, the medical outcome of an elective or spontaneous abortion, stillbirth or congenital anomaly is considered a serious adverse event and must be reported to AbbVie within 24 hours of the site becoming aware of the event.

